### 3.3.3. Sample Size and Power

Approximately, 520 participants will be enrolled at an evenly allocated ratio across the 13 treatment arms for adults ≥18 to <50 years of age, with 40 participants planned for each arm. Approximately 40 participants in each group receiving an investigational injection have approximately 80.5% (or 87.1%) probability to observe at least 1 participant with an AE given the true underlying incidence rate of AE is 4% (or 5%) (Table 10).

**Table 10 Sample Size Determination (Part 2)**

Sample Size	True AE Rate	Probability of 0 AEs	Power to Detect at Least 1 AE
40	2.0%	44.6%	55.4%
40	3.0%	29.6%	70.4%
40	4.0%	19.5%	80.5%
40	5.0%	12.9%	87.1%

### **3.3.4. Randomization**

Participants will be randomized (in equal allocation ratio) into the investigational treatment arms, stratified by influenza vaccine status in the most recent influenza season (received or not received since Sept 2023).

### **3.4. Blinding and Unblinding**

The planned analyses including a Day 29 interim analysis are described in Section 3.6.6 of this SAP. For further details on preidentified sponsor and CRO team members (identified by role), and the level of unblinding (treatment group level unblinding and/or subject level unblinding) at the IAs and the Final analysis, please refer to the study Data Blinding Plan.

## **3.5. Analysis Sets**

### **3.5.1. Randomization Set**

See Section 2.5.1 for details.

### **3.5.2. Full Analysis Set (FAS)**

See Section 2.5.2 for details.

### **3.5.3. Per Protocol (PP) Set**

The PP Set in Part 2 consists of all participants in the FAS who comply with the injection schedule, comply with the timings of immunogenicity blood sampling to have a Baseline and at least 1 post-injection assessment at Day 29 (-7 to +14 days), have no documented infection (confirmed by RT-PCR test) of either influenza or SARS-CoV-2 on Day 1, have no major dosing error, and have no major protocol deviations or conditions/medications that affect the immune

response. The PP Set will be used as the primary analysis set for analyses of immunogenicity unless otherwise specified. Participants will be analyzed according to the group to which they were randomized.

The major dosing error ranges, available in Table 11, will be used to determine participant exclusion from the PP analysis populations:

**Table 11 Exclusion Condition for Dosing Errors (Part 2)**

Randomized Group	Exclusion Conditions
mRNA-1083 CCI (cc1 µg)	Any of the following received: mRNA-1083 CCI ≤ CCI µg OR mRNA-1083 CCI > CCI µg OR mRNA-1083 CCI OR mRNA-1010 CCI OR mRNA-1283.815 OR mRNA-1273.815 OR Fluarix
mRNA-1083 CCI (cc1 µg)	Any of the following received: mRNA-1083 CCI ≤ CCI µg OR mRNA-1083 CCI > CCI µg OR mRNA-1083 CCI OR mRNA-1010 CCI OR mRNA-1283.815 OR mRNA-1273.815 OR Fluarix
mRNA-1083 CCI (cc1 µg)	Any of the following received: mRNA-1083 CCI ≤ CCI µg OR mRNA-1083 CCI > CCI µg OR mRNA-1083 CCI OR mRNA-1010 CCI OR mRNA-1283.815 OR mRNA-1273.815 OR Fluarix
mRNA-1083 CCI (cc1 µg)	Any of the following received: mRNA-1083 CCI ≤ CCI µg OR mRNA-1083 CCI > CCI µg OR mRNA-1083 CCI OR mRNA-1010 CCI OR mRNA-1283.815 OR mRNA-1273.815 OR Fluarix
mRNA-1083 CCI (cc1 µg)	Any of the following received: mRNA-1083 CCI ≤ CCI µg OR mRNA-1083 CCI > CCI µg OR mRNA-1083 CCI OR mRNA-1010 CCI OR mRNA-1283.815 OR mRNA-1273.815 OR Fluarix
mRNA-1083 CCI (cc1 µg)	Any of the following received: mRNA-1083 CCI ≤ CCI µg OR mRNA-1083 CCI > CCI µg OR mRNA-1083 CCI OR mRNA-1010 CCI OR mRNA-1283.815 OR mRNA-1273.815 OR Fluarix
mRNA-1083 CCI (cc1 µg)	Any of the following received: mRNA-1083 CCI ≤ CCI µg OR mRNA-1083 CCI > CCI µg OR mRNA-1083 CCI OR mRNA-1010 CCI OR mRNA-1283.815 OR mRNA-1273.815 OR Fluarix
mRNA-1083 CCI (cc1 µg)	Any of the following received: mRNA-1083 CCI ≤ CCI µg OR mRNA-1083 CCI > CCI µg OR mRNA-1083 CCI OR mRNA-1010 CCI OR mRNA-1283.815 OR mRNA-1273.815 OR Fluarix
mRNA-1010 CCI (cc1 µg)	Any of the following received: mRNA-1010 CCI ≤ CCI µg OR mRNA-1010 CCI > CCI µg OR mRNA-1083 CCI OR mRNA-1083 CCI OR mRNA-1283.815 OR mRNA-1273.815 OR Fluarix
mRNA-1010 CCI (cc1 µg)	Any of the following received: mRNA-1010 CCI ≤ CCI µg OR mRNA-1010 CCI > CCI µg OR mRNA-1083 CCI OR mRNA-1083 CCI OR mRNA-1283.815 OR mRNA-1273.815 OR Fluarix
mRNA-1283.815 CCI (cc1 µg)	Any of the following received: mRNA-1283.815 CCI ≤ CCI µg OR mRNA-1283.815 CCI > CCI µg OR

Randomized Group	Exclusion Conditions
	mRNA-1083 CCI OR mRNA-1083 CCI OR mRNA-1010 CCI OR mRNA-1273.815 OR Fluarix
mRNA-1273.815 (CCI $\mu$ g)	Any of the following received: mRNA-1273.815 $\leq$ CCI $\mu$ g OR mRNA-1273.815 > CCI $\mu$ g OR mRNA-1083 CCI OR mRNA-1083 CCI OR mRNA-1010 CCI OR mRNA-1283.815 OR Fluarix
Fluarix	Any of the following received: Fluarix $\leq$ 30 $\mu$ g OR mRNA-1083 CCI OR mRNA-1083 CCI OR mRNA-1010 CCI OR mRNA-1283.815 OR mRNA-1273.815

### 3.5.4. Safety Set

See Section 2.5.4 for details. Participants will be included in the vaccination group corresponding to what they actually received according to the as treated scheme given below in Table 12.

**Table 12 As Treated Grouping Scheme (Part 2)**

Group Name	Inclusion condition
mRNA-1083 CCI (CCI $\mu$ g)	Any dose of mRNA-1083 CCI > CCI $\mu$ g
mRNA-1083 (CCI $\mu$ g)	Any dose of mRNA-1083 CCI > CCI $\mu$ g and $\leq$ CCI $\mu$ g
mRNA-1083 (CCI $\mu$ g)	Any dose of mRNA-1083 > CCI $\mu$ g and $\leq$ CCI $\mu$ g
mRNA-1083 (CCI $\mu$ g)	Any dose of mRNA-1083 $\leq$ CCI $\mu$ g
mRNA-1083 (CCI $\mu$ g)	Any dose of mRNA-1083 > CCI $\mu$ g
mRNA-1083 (CCI $\mu$ g)	Any dose of mRNA-1083 CCI > CCI $\mu$ g and $\leq$ CCI $\mu$ g
mRNA-1083 (CCI $\mu$ g)	Any dose of mRNA-1083 > CCI $\mu$ g and $\leq$ CCI $\mu$ g
mRNA-1083 (CCI $\mu$ g)	Any dose of mRNA-1083 $\leq$ CCI $\mu$ g
mRNA-1010 (CCI $\mu$ g)	Any dose of mRNA-1010 CCI > CCI $\mu$ g
mRNA-1010 (CCI $\mu$ g)	Any dose of mRNA-1010 CCI $\leq$ CCI $\mu$ g
mRNA-1283.815 (CCI $\mu$ g)	Any dose of mRNA-1283.815
mRNA-1273.815 (CCI $\mu$ g)	Any dose of mRNA-1273.815
Fluarix	Any dose of Fluarix

### 3.5.5. Solicited Safety Set

See Section 2.5.5 for details.

## 3.6. Statistical Analysis

The SoA is provided in the Appendix A.

### 3.6.1. General Considerations

See Section 2.6.1 for details.

**For calculation regarding antibody levels/titers**, antibody values reported as below the lower limit of quantification (LLOQ) will be replaced by  $0.5 \times \text{LLOQ}$ . Values reported as above the upper limit of quantification (ULOQ) will be converted to the ULOQ. Missing results will not be imputed.

**Table layouts** will be presented according to vaccination group. First for the overall participants, then by subgroups as given in Table 13.

For Part 2, the following vaccination groups will be used for summary purposes for tables and figures outputs:

- Fluarix
- mRNA-1010 [REDACTED]  $\mu\text{g}$
- mRNA-1010 [REDACTED]  $\mu\text{g}$
- mRNA-1273.815 [REDACTED]  $\mu\text{g}$
- mRNA-1283.815 [REDACTED]  $\mu\text{g}$
- mRNA-1083 [REDACTED]  $\mu\text{g}$
- All mRNA-1083 [REDACTED] (all mRNA-1083 [REDACTED] vaccination groups combined; applicable to safety and reactogenicity analyses only)
- All mRNA-1083 [REDACTED] (all mRNA-1083 [REDACTED] vaccination groups combined; applicable to safety and reactogenicity analyses only)
- Overall (All vaccination groups combined; details are available below)

The “Overall” combined group will be presented for baseline summaries such as participant disposition, demographic summaries, concordance of randomization stratum, etc. as well as

major protocol deviation, medical history, concomitant medication and study duration summaries.

**Subgroups:** For Part 2, the following subgroups will be used for summary purposes, where indicated in this SAP. Unless otherwise specified, all subgroups are based on eCRF.

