**The following analysis periods** of safety analyses will be used:

- Throughout the Study: from the day of vaccination (Day 1) and continues through the earliest date of (study completion, discontinuation from the study, or death).
- Within 7 days after injection: this period includes the day of vaccination and 6 subsequent days, or up to the study discontinuation or death, whichever comes earlier. This analysis period will be used for solicited local and systemic AR that occur during this time.
- Up to 28 days after injection: starts from the day of vaccination (Day 1) and spans 28 days to include the day of vaccination and 27 subsequent days, or up to the study discontinuation or death, whichever comes earlier. This analysis period will be used as the primary analysis period for safety analyses including unsolicited AE, except for solicited AR, unless specified otherwise.

**Study day relative to the injection** will be calculated as below:

- a) study day prior to the injection will be calculated as: date of assessment/event – date of the injection (resulting in negative study day);
- b) study day on or after the date of the injection will be calculated as: date of assessment/event – date of the injection + 1;

**Duration of an event** will be calculated as (Event end date – Event start date +1). The duration of the study will be calculated for the participants included in the safety set:

- Since randomization: date of last visit (as recorded on End of Study [EoS] eCRF) – date of randomization + 1,

- Since study injection: date of last visit (as recorded on End of Study [EoS] eCRF) – date of injection + 1.

If the last visit date on the EoS eCRF page is missing, then the latest of either the cut-off date or the last available visit date will be employed. The durations of solicited ARs will be calculated as: reaction end date – reaction start date +1, regardless of whether the AR is intermittent or continued or if the solicited AR continues beyond 7 days.

**For calculation regarding antibody levels/titers**, antibody values reported as below the lower limit of quantification (LLOQ) will be replaced by  $0.5 \times \text{LLOQ}$ . Values that are greater than the upper limit of quantification (ULOQ) will be converted to the ULOQ if actual values are not available. Missing results will not be imputed.

**Unscheduled visits:** Unscheduled visit measurements will be included in the analyses as follows:

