### 3.2. Study Endpoints

#### 3.2.1. Primary Endpoints

- Solicited local and systemic ARs through 7 days after injection

- Unsolicited AEs through 28 days after injection
- Unsolicited Severe AEs through 28 days after injection
- Unsolicited MAAEs from Day 1 to Day 181/EoS
- Unsolicited AESIs from Day 1 to Day 181/EoS
- SAEs from Day 1 to Day 181/EoS
- Unsolicited AEs leading to discontinuation from Day 1 to Day 181/EoS
- GMT and GMFR at Day 29 compared to Day 1 by HAI assay for influenza and by PsVNA for SARS-CoV-2
- Influenza: Percentage of participants with seroconversion, defined as a Day 29 titer **CCI** if Baseline is **CCI** or a 4-fold or greater rise if Baseline is **CCI** in anti-HA antibodies measured by HAI assay
- SARS-CoV-2: Percentage of participants with seroresponse, defined as a Day 29 titer  $\geq 4$ -fold if Baseline is  $\geq \text{LLOQ}$  or  $\geq 4 \times \text{LLOQ}$  if Baseline titer is  $< \text{LLOQ}$  in nAb titers measured by PsVNA

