### 3.3.2. Statistical Hypotheses

See Section 2.3.2 for details.

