**Table 14 Covariates Included in Different ANCOVA Models (Part 2)**

Assay	Subgroup	Covariate(s)
PsVNA	Overall	Log-transformed baseline antibody value, Influenza Vaccine Status Since Sept 2023 (IRT)
	Overall	Log-transformed baseline antibody value
	Covid Vaccine Status Since Sept 2023: Received	Log-transformed baseline antibody value
	Covid Vaccine Status Since Sept 2023: Not Received	Log-transformed baseline antibody value
	Baseline SARS-CoV2 Status: Positive	Log-transformed baseline antibody value
	Baseline SARS-CoV2 Status: Negative	Log-transformed baseline antibody value
HAI	Overall	Log-transformed baseline antibody value, Influenza Vaccine Status Since Sept 2023 (IRT)
	Overall	Log-transformed baseline antibody value, Influenza Vaccine Status Since Sept 2023 (EDC)
	Influenza Vaccine Status Since Sept 2023 (EDC): Received	Log-transformed baseline antibody value
	Influenza Vaccine Status Since Sept 2023 (EDC): Not Received	Log-transformed baseline antibody value

For each pair of between-group comparison specified in Table 15, the GMR between the two treatment groups in each pair will be estimated from the ANCOVA model, with its 2-sided 95% CI provided accordingly.

Seroconversion rate (SCR) for influenza from Baseline will be summarized at Day 29 with its 2-sided 95% CI using the Clopper-Pearson method for participants in the groups receiving mRNA-1083, mRNA-1010 or Fluarix.

- SCR at Day 29 is defined as the percentage of participants with a Day 29 titer **CCI** if Baseline is **CCI** or a 4-fold or greater rise if Baseline is **CCI** in anti-HA antibodies measured by HAI assay

Seroresponse rate (SRR) for SARS-CoV-2 from Baseline will be summarized at Day 29 with its 2-sided 95% CI using the Clopper-Pearson method for participants in the groups receiving mRNA-1083, mRNA-1283.815 or mRNA-1273.815.

- SRR at Day 29 is defined as the proportion of participants with a Day 29 titer  $\geq$  4-fold if Baseline is  $\geq$  LLOQ or  $\geq 4 \times$  LLOQ if Baseline titer is  $<$  LLOQ in nAb titers measured by PsVNA.

Additional comparisons or analysis statistics will be provided by treatment arm at Day 29 for the influenza and SARS-CoV-2 endpoints. For each pair of between-group comparison specified in Table 15, the difference of seroresponse/seroconversion rate (SRR/SCR) between the two treatment groups in each pair will be provided, with its 2-sided 95% CI estimated using Miettinen-Nurminen method.

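### The SAP's rule for titers above the ULOQ differs between Part 1 and Part 2 without explanation, and the Part 2 wording can be read as capping measured values

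*SAP*

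**What the plan says.** SAP section 2.6.1 (Part 1) reads "Values that are greater than the upper limit of quantification (ULOQ) will be converted to the ULOQ if actual values are not available". SAP section 3.6.1 (Part 2) opens with "See Section 2.6.1 for details", then restates the paragraph on antibody titers in full. The sentences on results below the LLOQ and on missing results carry the same rules as in Part 1. The ULOQ sentence does not: "Values reported as above the upper limit of quantification (ULOQ) will be converted to the ULOQ". The condition about actual values is gone.

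Both parts measure HAI and PsVNA titers (SAP 2.6.4 and 3.6.4). The SAP's version table records the addition of Part 2 and a later change to the Table 14 covariates, but nothing about the ULOQ. SAP section 4 declares no change from the protocol's planned analysis.

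In Part 2 the immunogenicity endpoints are primary. SAP 3.2.1 lists "GMT and GMFR at Day 29 compared to Day 1 by HAI assay for influenza and by PsVNA for SARS-CoV-2", together with seroconversion and seroresponse at Day 29. Under those endpoints, SAP 3.6.4.1 adds that "the GMR between the two treatment groups in each pair will be estimated from the ANCOVA model".

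**The concern.** A later, specific rule normally displaces a general cross-reference. A programmer working from section 3.6.1 could therefore reasonably set every result above the ULOQ to the ULOQ, including results for which the laboratory has supplied a number. The Part 1 condition suggests that the sponsor thought such numbers possible for these assays.

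The less protective wording falls on the part where the endpoints rank higher, since Day 29 titers were secondary in Part 1. Part 2 compares eight mRNA-1083 arms, covering two compositions at four dose levels each, with one another's controls. A ceiling takes most from the arms with the highest titers, which are the ones that a dose comparison is meant to separate. It also limits the fold rise that a participant with a high baseline can show.

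**Working it through.** **1. The plan's own figure.** The only numerical design statement for Part 2 concerns adverse events. 520/13 = 40 per arm, which agrees with "with 40 participants planned for each arm". 1 − 0.96^40 = 80.5% and 1 − 0.95^40 = 87.1%, as stated. Neither figure bears on the ULOQ, and the documents give none that does.

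**2. The two rules by case.**

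| Laboratory result | Part 1 rule | Part 2 rule as worded |
|---|---|---|
| Within range | unchanged | unchanged |
| Above ULOQ, no number given | set to ULOQ | set to ULOQ |
| Above ULOQ, number given | number used | open: can be read as set to ULOQ |

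The rules can differ only in the last row.

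**3. Effect on a GMR if that row is capped.** Assumptions (none is in the documents): log10 titers are normal, the SD is the same in both arms, and a share s of the reference arm lies above the ULOQ. With c = log10 ULOQ and a = (c − μ)/σ, the capped mean is

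E[min(X, c)] = μΦ(a) − σφ(a) + c(1 − Φ(a)),

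and the capped GMR is 10 raised to the difference in capped means.

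Worked case: σ = 0.5, s = 10%, true GMR 2.0. Set the reference mean to 0, so c = 0.5 × 1.2816 = 0.641.
- Reference arm: −0.5 × 0.1755 + 0.641 × 0.10 = −0.024.
- Higher arm: μ = log10 2 = 0.301, a = 0.680, Φ(a) = 0.752, φ(a) = 0.317. The capped mean is 0.226 − 0.158 + 0.159 = 0.227.
- Difference 0.251, so the capped GMR is 10^0.251 = 1.78.

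| Reference arm above ULOQ (assumed) | Participants of 40 | True 1.5 reported as | True 2.0 reported as | Higher arm above ULOQ when true GMR is 2.0 |
|---|---|---|---|---|
| 1% | 0.4 | 1.49 | 1.97 | 4.2% |
| 5% | 2 | 1.46 | 1.88 | 14.9% |
| 10% | 4 | 1.42 | 1.78 | 24.8% |
| 20% | 8 | 1.35 | 1.63 | 40.5% |

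At 10%, varying σ from 0.3 to 0.7 moves the true-2.0 result between 1.71 and 1.81. A simulated baseline-adjusted ANCOVA (400,000 per arm, σ = 0.5, baseline correlation 0.5, both visits capped) agrees: a true 1.5 gives 1.49, 1.46, 1.42 and 1.36.

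**4. Limits on direction.** With equal SDs, a true GMR of 1 stays at 1.00. With SD 0.6 in the numerator arm and 0.4 in the reference arm, a true 1.0 becomes 0.968, 0.927 and 0.898 at 1, 5 and 10%, and a true 0.9 becomes 0.876, 0.845 and 0.825. The movement is then away from 1.

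**5. Effect on a 4-fold rise.** If Day 29 cannot exceed the ULOQ and baseline B is above ULOQ/4, the recorded rise is at most ULOQ/B, which is less than 4. This is arithmetic and needs no model. In the same simulation, with an assumed reference-arm rise of 5- or 10-fold and a true GMR of 1 or 1.5, the loss in the share of participants with a 4-fold rise was:
- 1% above ULOQ: at most 0.1 percentage points
- 5%: 0.2 to 0.8 points
- 10%: 0.6 to 2.2 points
- 20%: 2 to 6 points

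**The case against.** The strongest reply is that the two sentences may mean the same thing. Part 2 speaks of values reported as above the limit, in parallel with its phrase for results below the LLOQ. That can refer to results returned only as greater than the ULOQ, with no number to overwrite. Part 1 speaks of values greater than the limit, which can include numeric results and so needs the extra clause. Section 3.6.1 also begins by pointing to section 2.6.1, where the conditional rule sits. This stands as far as it goes: a reader might infer that Part 2 discards measured data, and the text does not establish that. But neither reading is excluded, and the rule governs primary variables.

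Other stronger inferences also fail.
- **Every GMR is biased towards 1.** Step 4 shows this is false for a true GMR of 1 and with unequal SDs.
- **The GMR is a primary endpoint.** It is an analysis reported under the primary endpoints. SAP 3.3.2 says only "See Section 2.3.2 for details", and section 2.3.2 plans no formal test for safety and reactogenicity and sets nothing for immunogenicity. No margin or power depends on the GMR.
- **High baselines are certain.** Part 2 participants have had at least 2 COVID-19 vaccine doses, but the last was at least 90 days before Day 1. Influenza vaccination within 150 days is excluded, as are known SARS-CoV-2 infection within 90 days and a positive influenza test within 150 days. Elevated baselines are plausible; nothing shows baselines above ULOQ/4.
- **The ceiling on seroresponse is peculiar to Part 2.** Part 1 has it too wherever no actual value exists.

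The planned Part 2 listing shows antibody levels beside the LLOQ and ULOQ, which would help to identify results at the limit. It does not settle which value enters the analysis.

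**Conclusion.** The SAP gives two different ULOQ rules for the same assays and does not explain the difference. The Part 2 rule is open to a reading that caps measured titers in primary endpoints. That much rests on the text alone.

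The consequence is conditional. It needs titers above the ULOQ and numeric results beyond it, and neither is documented. If both exist and the values are capped, Day 29 GMT and GMFR fall most in the highest-titer arms. With similar SDs, a GMR that differs from 1 usually shrinks. The shrinkage is negligible at 1% of the reference arm above the ULOQ and material at 10 to 20%, although for a true GMR of 2.0 those last cases already put about 25 to 41% of the higher arm beyond the assay range. If no titer exceeds the ULOQ, or the laboratory reports no number above it, the effect is nil. The point merits correction because the plan is ambiguous on a primary variable and the remedy is already in the SAP; a demonstrated bias is not claimed.

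**What to change.** In SAP section 3.6.1, replace the Part 2 ULOQ sentence with the Part 1 rule, so that a result is set to the ULOQ only when no measured value exists. In the immunogenicity summaries, report by arm, assay and visit the number of results set to the ULOQ, so that readers can judge whether the ceiling matters. Make the change before database lock and unblinding; for the Day 29 endpoints, the relevant lock is the one for the Part 2 interim analysis.

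The cost is one clause and one line of counts. No design figure changes. If the laboratory supplies no numbers above the ULOQ, the new wording alters no result.

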**Table 13 Definition for Subgroups (Part 2)**

Subgroup Variable	Categories
Influenza Vaccine Status Since Sept 2023	Received Not Received
Covid Vaccine Status Since Sept 2023	Received Not Received
Baseline SARS-CoV-2 Status	Positive Negative

### **3.6.2. Background Characteristics**

#### **3.6.2.1. Participant Disposition**

See Section 2.6.2.1 for details.

#### **3.6.2.2. Demographics and Baseline Characteristics**

Descriptive statistics for age, weight, height, and BMI are described in Section 2.6.2.2.

The number and percentage of participants will be provided for the following categorical variables:

- Sex (Male, Female)
- Race (White, Black or African American, Asian, American Indian or Alaska Native, Native Hawaiian or Other Pacific Islander, Multiracial, Other, Not Reported, Unknown)
- Ethnicity (Hispanic or Latino, Not Hispanic or Latino, Not Reported, Unknown)
- Influenza vaccine status in the most recent influenza season (received or not received since Sept 2023) per eCRF
- Covid vaccine status (received or not received since Sept 2023) per eCRF
- Childbearing Potential for female participants (Yes/No) and reason if “No”
- Baseline SARS-CoV-2 RT-PCR Results (positive, negative, or missing)
- Baseline Elecsys Anti-SARS-CoV2 Results (positive, negative, or missing)

- Baseline SARS-CoV-2 Status (positive, negative, or missing)

The summaries will be provided separately for all analysis sets (except Randomization Set and Solicited Safety Set) defined in the Section 3.5. The number and percentage of participants randomized by country and site will be provided as well.

### **3.6.2.3. Medical History**

See Section 2.6.2.3 for details.

### **3.6.2.4. Prior and Concomitant Medications**

See Section 2.6.2.4 for details.

### **3.6.2.5. Study Exposure**

See Section 2.6.2.5 for details.

